### 13.2 Sample Size

The primary endpoint will be delayed recall, as measured by the relative (percent) change in HVLTR delayed recall score from the start of treatment to 3 months after the start of treatment.

The sample size calculation will address the specific primary hypothesis that WBRT-HA/SIB reduces decline in delayed recall (from baseline to 3 months). We do not expect improvement in delayed recall; at best, we anticipate a preservation of delayed recall. Data from a randomized trial showed that the decline in HVLTR delayed recall score was 64% at 4 months for those getting whole brain radiation for brain metastases (Chang et al., 2009). We anticipate that WBRT-HA/SIB will have better delayed recall functioning at 3 months than WBRT alone. Detecting a 30% average relative loss due to WBRT-HA/SIB suggests a 50% relative improvement over previous results. The null and alternative hypotheses are:

$$H_0: \Delta HVLTR = 0.60 \text{ vs. } H_A: \Delta HVLTR \leq 0.30$$

$\Delta$ HVLT-R is the mean of relative decline between baseline and 3 month after treatment in this patient population. For patient individual i, the relative decline is calculated as follows:  $\Delta$ HVLT-Ri = ( HVLT-Ri0 - HVLT-Ri3 ) / HVLT-Ri0 , where HVLT-Ri0 and HVLT-Ri3 denote individual patient scores at baseline and 3 months after treatment, respectively.

Initial sample size calculation:

Based on the one-sided one sample t-test, assuming a standard deviation of 41%, with alpha=0.05 (one-sided), a total of 9 analyzable patients would ensure 80% statistical power to detect a 30% average relative loss in delayed recall at 3 months. Assuming a death rate of 60% prior to 3 months and a 10% in-evaluable rate, the target sample size will be 34 registered patients.

Sample size re-estimation based on internal pilot study:

The internal pilot consists of 32 patients enrolled at baseline, among which 9 patients have complete information on HVLT-R delayed recall score at the start of treatment and 3 months after the start of treatment. For the 9 patients, the mean and standard error of relative (percent) change (decline) in HVLT-R delayed recall score is 31% and 51%. We re-estimate the required sample size using the updated standard error.

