Based on the one-sided one sample t-test, assuming a standard deviation of 51%, with alpha=0.05 (one-sided), a total of 18 analyzable patients would ensure 80% statistical power to detect a 30% average relative loss in delayed recall at 3 months. Assuming a death rate of 60% prior to 3 months and a 10% in-evaluable rate, the target sample size will be 50 registered patients. Therefore, additional 18 patients need to be recruited at the second stage.

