### 13.3 Analysis Plan

#### 13.3.1 Primary Endpoint

The primary endpoint is delayed recall, as determined by the relative change in HVLT-R delayed recall score from the start of treatment to 3 months after the start of treatment. To test the null hypothesis H0, the primary endpoint will be analyzed using the one-sided one sample t-Test with a significance level of 0.05.

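### Section 13.2 calls the pilot's 51% a standard error, then uses it as the standard deviation; it is probably a mislabelled standard deviation, and the planned t-test with 18 patients then has about 77% power, not 80%.

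*Combined protocol and SAP*

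**What the plan says.** The current target comes from the sample size re-estimation in Section 13.2 (Sample Size). Of 32 pilot patients enrolled, "9 patients have complete information on HVLT-R delayed recall score at the start of treatment and 3 months after the start of treatment". For these nine, "the mean and standard error of relative (percent) change (decline) in HVLT-R delayed recall score is 31% and 51" (per cent). The text continues: "We re-estimate the required sample size using the updated standard error".

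The following paragraph does the calculation "assuming a standard deviation of 51%, with alpha=0.05 (one-sided), a total of 18 analyzable patients would ensure 80% statistical power". Allowing for 60% deaths before 3 months and 10% in-evaluable patients, it sets the target at 50 registered.

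The initial calculation, earlier in the same section, used a figure of 41% and called it a standard deviation. The hypotheses set a mean relative decline of 0.60 against 0.30 or less. Section 13.3.1 says that "the primary endpoint will be analyzed using the one-sided one sample t-Test with a significance level of 0.05".

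**The concern.** A standard error and a standard deviation are different quantities. With nine patients they differ by a factor of three, so 51% cannot be both. The plan uses the first name in two consecutive sentences, the second of which says that this is the input to the re-estimation, and then uses the other name in the calculation. No other section settles which is meant, and no individual pilot values or other measure of spread are given.

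The figure is not background. Effect, alpha, power and attrition are the same in the initial and the revised calculation; the spread is the input that the plan says it updated. The 18 analyzable, the 50 registered and the 18 additional patients all follow from it. A factor of three in the standard deviation is a factor of nine in the required number.

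The label also governs how the pilot is read. Against the null of 0.60, the pilot mean of 0.31 lies (0.31 − 0.60)/0.17 = −1.71 standard errors away if 51% is the standard deviation, and (0.31 − 0.60)/0.51 = −0.57 if it is the standard error. Section 1.7 says that this study should inform whether a phase III trial is warranted and how it would be planned, so a reader could carry the wrong variance forward.

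**Working it through.** **Inputs, all from Section 13.2 (Sample Size) unless noted.** Difference to detect: 0.60 − 0.30 = 0.30. One-sided alpha 0.05; target power 80%. Pilot: n = 9, mean 31%, spread 51%. Test: one-sided one-sample t-test (Section 13.3.1). Attrition: 60% deaths, 10% in-evaluable.

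**1. Reproducing the plan's figure.** Normal formula: n = ((z₀.₉₅ + z₀.₈₀) × SD / 0.30)².
- SD 0.51: ((1.645 + 0.842) × 0.51/0.30)² = 17.87, so 18.
- Registered: 18 / (0.40 × 0.90) = 18 / 0.36 = 50.

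Both match the plan. The calculation therefore used 51% as the standard deviation, with the normal formula.

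**2. What the two labels imply at n = 9.**
- If 51% is the SD: SE = 51% / √9 = 17%.
- If 51% is the SE: SD = 51% × √9 = 153%.

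**3. Power of 18 patients.** The t column uses the noncentral t distribution with 17 degrees of freedom and noncentrality 0.30 × √18 / SD.

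| Reading of 51% | SD | Noncentrality | Power, normal | Power, t-test | n for 80%, normal | n for 80%, t-test |
|---|---|---|---|---|---|---|
| Standard deviation | 51% | 2.50 | 80.3% | 77.3% | 18 | 20 |
| Standard error | 153% | 0.83 | 20.8% | 19.9% | 161 | 163 |

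Even on the first reading, the test that the plan names falls short of the stated 80%, because 18 comes from the normal formula. With 19 patients the t-test gives 79.4%, and with 20 it gives 81.3%.

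**4. Which reading fits the documents.** The only figure that could have been updated is the 41% of the initial calculation, which is called a standard deviation, and 51% is a natural successor to it.

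**5. What the standard-error reading would need.** By the plan's formula, relative decline cannot exceed 100%. Write y = 1 − decline, the ratio of the 3-month score to baseline, so y ≥ 0. Nine patients with mean decline 0.31 and SD 1.53 have:
- Σy = 9 × 0.69 = 6.21
- Σy² = 8 × 1.53² + 9 × 0.69² = 18.73 + 4.28 = 23.01

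The largest y is smallest when one other patient holds all the rest and seven score zero: M² + (6.21 − M)² = 23.01, which gives M = 4.47. So one patient must rise to at least about 4.5 times baseline, a gain of about 347%. At that minimum the other eight average y = (6.21 − 4.47)/8 = 0.22, a loss of about 78%; a larger M makes their average loss greater. Delayed recall is a count out of 12 words (Appendix III), and 12/4.47 = 2.7, so the improver's baseline is at most 2 words. Allowing for rounding of the 31% and 51%, the gain is still at least 338% and the others' mean loss at least 76%.

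**6. It is still possible.** In a constructed set, one patient goes from 2 words to 9 (decline −3.50), one from 3 to 5 (−0.667), and seven fall to zero (+1 each). The mean decline is (7 − 4.167)/9 = 0.315. The squared deviations sum to 7 × 0.685² + 3.815² + 0.981² = 18.80, so SD = √(18.80/8) = 1.53 and SE = 0.51. The published summary alone cannot exclude such data.

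**The case against.** The strongest case against raising this is that it is a slip of one word. The authors say they are updating a figure, and the figure updated was a standard deviation. The paragraph that does the calculation names the quantity correctly. Both targets reproduce. The rival reading needs one extreme improver and eight patients who on average lose 78% or more, worse than the 64% decline that the plan cites for whole-brain radiation, in a protocol that expects no improvement in delayed recall. On the likely reading the enrolment target, the analysis and the conduct of the trial are untouched, and the gap between 77.3% and 80% comes from the choice of formula, not from the label.

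Most of this stands, and it is why the point is minor. Two things remain. The pilot standard error as printed is then three times too large (51% against 17%), so the text needs correcting whichever label is right. And the stated power does not belong to the test that Section 13.3.1 specifies.

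In the other direction, a reader who takes the words standard error at face value might infer that the trial has about 20% power and needs some 160 analyzable patients. The arithmetic is right on that premise, but the documents do not support the premise: it conflicts with the paragraph that does the calculation and with the figure being updated, and it requires the improbable data pattern in step 5.

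**Conclusion.** The inconsistency is certain: Section 13.2 gives one number two incompatible names, in the input that sets the current target. The likely explanation is a mislabelled standard deviation. On that reading 18 analyzable and 50 registered stand as the plan derived them, the pilot standard error is 17%, and 18 patients give 77.3% power under the specified one-sided t-test, against 80.3% under the normal approximation and 80% as stated.

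The figure of about 20% power is conditional on the pilot data showing that 51% is the standard error, and should not be read as the probable power of the trial. The published text makes that unlikely without ruling it out; the nine pilot values would settle it.

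These figures take the plan's own difference of 0.30, one-sided alpha of 0.05 and 18 analyzable patients as given, and assume approximately normal relative changes, as the t-test calculation does. Severity is minor, unless the data check confirms the standard-error reading; the stated basis of the sample size would then be materially wrong.

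**What to change.** Recompute the standard deviation of relative decline from the nine pilot values that the sponsor already holds.

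- **If it is 51%:** in Section 13.2, replace standard error by standard deviation in both pilot sentences. If a standard error is wanted as well, give it as 17%. Restate the power of 18 analyzable patients under the one-sided t-test as about 77%, or say explicitly that 80% is a normal approximation.
- **If 51% proves to be the standard error:** replace the standard deviation in the calculation paragraph by 153% and restate the power of 18 analyzable patients as about 20%.

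The cost is one recalculation from existing data and a short wording amendment. The stated power becomes a little less favourable on the likely reading. No additional enrolment, procedure or change to the analysis is asked for.

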## SCHEMA

### Patient Population: (See Section 3.0 for Eligibility)

1. Pathologically proven diagnosis of a non-hematopoietic malignancy other than small cell lung cancer and germ cell malignancy.
2. Patients with less than 9 discrete metastases on MRI.
3. Measurable brain metastasis outside a 5-mm margin around either hippocampus
4. Have not been treated with SRS or surgical resection.
5. Patients with progressive brain metastases beyond a brain lesion previously treated with radiosurgery are eligible so long as at least 3 months has transpired from the radiosurgery procedure prior to registration.
6. RTOG RPA class I or II
7. Life expectancy of at least 3 months
8. Age  $\geq$  18 years
9. Karnofsky performance status  $\geq$  70
10. Two or fewer sites of uncontrolled or untreated sites of extracranial metastases
11. No active pulmonary, gastrointestinal, genitourinary or other serious infection at time of enrollment

Required sample size: 102

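### Section 13.2 states 80% power from 18 analyzable patients out of 50 registered; the named t-test gives about 77% at 18, 50 registrations may yield fewer than 18, and the Schema still requires 102

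*Combined protocol and SAP*

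**What the plan says.** The re-estimation in section 13.2 works from a one-sided one-sample t-test, "assuming a standard deviation of 51%, with alpha=0.05 (one-sided"), and a null mean relative decline of 0.60 against an alternative of 0.30. It states that "a total of 18 analyzable patients would ensure 80% statistical power to detect a 30% average relative loss". Section 13.3.1 fixes the same test for the analysis: "the primary endpoint will be analyzed using the one-sided one sample t-Test with a significance level of 0.05".

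On accrual, 13.2 reports: "The internal pilot consists of 32 patients enrolled at baseline, among which 9 patients have complete information". It then sets the registration target: "Assuming a death rate of 60% prior to 3 months and a 10% in-evaluable rate, the target sample size will be 50 registered patients". It closes: "Therefore, additional 18 patients need to be recruited at the second stage".

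The Schema at the front of the document gives a different total: "Required sample size: 102".

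The 51% appears under two labels. The pilot paragraph reports it as a standard error and says "We re-estimate the required sample size using the updated standard error". The next paragraph uses the same figure as a standard deviation.

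**The concern.** There are three separate problems in one short calculation.

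- **Power.** The analyzable number does not come from the test that the plan names.
- **Yield.** The registration number is computed as if the trial were starting afresh, although 32 of the 50 patients are already enrolled and their analyzable count is reported. The re-estimation takes the SD from the pilot but ignores how many analyzable patients the pilot produced.
- **Total.** The Schema and 13.2 disagree on how many patients are required.

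This is the trial's only powered hypothesis. If the primary test is non-significant, the result will be read against a stated 80% power that the design does not deliver on its own assumptions. The two totals also leave the point at which accrual is complete in contradiction.

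**Working it through.** **Inputs, all from section 13.2 unless noted.** Null 0.60 and alternative 0.30, so the difference is 0.30. SD 0.51. One-sided alpha 0.05. Death before 3 months 60%, in-evaluable 10%, so the planned yield is 0.40 × 0.90 = 0.36. Pilot: 32 enrolled, 9 analyzable. Further recruitment: 18. Schema total: 102.

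**Step 1. Reproduce the plan's figures.** Normal approximation: n = (SD × (z₀.₉₅ + z₀.₈₀) / difference)² = (0.51 × 2.4865 / 0.30)² = 17.87, rounded up to 18, with power 80.3%. Registrations: 18 / 0.36 = 50. Further recruitment: 50 − 32 = 18. All three reproduce, but only with the normal approximation.

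**Step 2. Power under the named test.** For the t-test, power is the probability that a noncentral t variable with n − 1 degrees of freedom and noncentrality (0.30/0.51) × √n exceeds the central t critical value at one-sided 0.05.

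| Analyzable n | t-test power |
|---|---|
| 14 | 67.0% |
| 15 | 69.9% |
| 16 | 72.6% |
| 18 | 77.3% |
| 19 | 79.4% |
| 20 | 81.3% |

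So 18 falls 2.7 points short, and 20 is the first number above 80%.

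**Step 3. Expected analyzable number.** Let m be the number of pilot patients who had not yet reached the 3-month test when the 9 were counted. The plan does not give m. The expected total is 9 + (18 + m) × yield. Average power is the Step 2 power averaged over 9 + Binomial(18 + m, yield).

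| Assumption | Expected analyzable | Average power | Chance of at least 18 |
|---|---|---|---|
| m = 0, yield 36% | 15.5 | 70.8% | 16% |
| m = 3, yield 36% | 16.6 | 73.5% | 33% |
| m = 7, yield 36% | 18.0 | 76.8% | 57% |
| m = 0, yield 9/32 = 28% | 14.1 | 66.8% | 4% |

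Break-even for an expected 18 at 36%: m = (18 − 15.48) / 0.36 = 7. Average power first reaches 80% at m = 12 (80.4%; at m = 11 it is 79.7%). With m = 0, the 18 new registrations would have to supply 9 analyzable patients, a 50% yield. For comparison, if all 50 patients really were still to come, average power at 36% would be 76.3%.

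**Step 4. Does the pilot refute the 36%?** No. The planned yield from 32 patients is 32 × 0.36 = 11.5, and the probability of 9 or fewer is 0.23. The gap arises because the 50 is not conditioned on patients already observed; it does not show that the planned rate is wrong.

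**Step 5. The Schema total.** 102 × 0.36 = 36.7 analyzable, which matches neither the 18 nor the 50 of 13.2. It does not match the earlier target of 34 either.

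**Secondary checks.** If 51% were literally a standard error from 9 patients, the SD would be 0.51 × √9 = 153%, so this is probably a labelling slip. In the initial calculation (SD 41%), 9 analyzable patients give 64% t-test power, and 9/0.36 = 25, not 34. The 34 fits 12 analyzable (12/0.36 = 33.3).

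**The case against.** The strongest reply is that the t-test gap is small and swamped by uncertainty in the SD. The 51% comes from 9 patients, with a normal-theory 95% interval of about 34% to 98%. Over that interval, power at 18 patients runs from about 97% down to about 35%, and an SD of 49% would already give 80.2%. That is fair: the correction from 80% to 77% would not by itself change a decision. It is still a correction, because the plan states the power for a specific test and a specific SD, and the number does not follow from them.

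The second reply is that a shortfall in yield is not shown. The plan does not say that the other 23 pilot patients had died, dropped out or passed 3 months, and with enough of them pending the target is met. This also stands, and it limits the claim: the 67% to 71% range applies only if the pilot was complete, and its lower end also needs the 28% yield. What remains is that 13.2 neither gives the pending count nor uses the 9 already in hand, so its 50 cannot be verified.

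The third reply is that 102 is evidently stale, since 13.2 derives 50 step by step and nothing derives 102. That is likely, but it is a live contradiction in the Schema. The mismatch in the initial calculation is indeed minor: the plan already labels that calculation as initial, and its 9 may come from comparing 64% with 30% (normal approximation 8.99).

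**Conclusion.** The concern holds. On the plan's own test and inputs, 18 analyzable patients give 77.3% power, not 80%, and 20 are needed to exceed 80%. Whether 50 registrations deliver 18 depends on the unstated number of pilot patients still pending. At the planned 36% yield, the expected total is 15.5 with average power of about 71% if none was pending, and it reaches 18 only if 7 were. At the pilot's 28% with none pending, the figures are 14.1 and about 67%. The conflict between 102 and 50 depends on no assumption.

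All power figures assume that the SD is 51% and that patients yield analyzable data independently at the stated rate. The arithmetic is certain; the existence and size of a yield shortfall are conditional on the pending count.

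**What to change.** Keep 50 registrations and correct the text.

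1. In the re-estimation paragraph of 13.2, replace the 80% claim with: 18 analyzable patients give about 77% power (one-sided one-sample t-test, SD 51%).
2. After the statement on second-stage recruitment, report how many of the 32 pilot patients had not reached 3 months (m). Give the expected analyzable number as 9 + (18 + m) × a stated yield, with its power. For m = 0 this is 15.5 and about 71% at 36%, or 14.1 and about 67% at 28%. For m = 7 at 36% it is 18 and about 77%.
3. In the Schema, replace 102 with the 13.2 total.
4. Secondary: check the 51% against the data and relabel it as a standard deviation in the pilot paragraph. State that the initial calculation is superseded and that its 9 and 34 do not correspond.

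The cost is wording plus one count that the sponsor should already hold. No extra patients are required. The downside is that the stated power falls to 77%, or lower if few pilot patients were pending.

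### Second-stage recruitment of 18 counts the 32 pilot patients at the planned yield (11.5 analyzable) instead of the 9 reported, so unless some were still pending, 50 registrations give an expected 15.5 analyzable patients and about 71% power, not 18 and 80%.

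*Combined protocol and SAP*

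**What the plan says.** Section 13.2 (Sample Size) gives an initial calculation and then a re-estimation from an internal pilot. On the pilot's yield it says: "The internal pilot consists of 32 patients enrolled at baseline, among which 9 patients have complete information" on delayed recall at both time points. On what is updated: "We re-estimate the required sample size using the updated standard error". The new requirement is that "a total of 18 analyzable patients would ensure 80% statistical power to detect a 30% average relative loss", with the inputs "assuming a standard deviation of 51%, with alpha=0.05 (one-sided".

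The conversion to registrations uses the same attrition rates as the initial calculation: "Assuming a death rate of 60% prior to 3 months and a 10% in-evaluable rate, the target sample size will be 50 registered patients". The next sentence subtracts the 32 already enrolled: "Therefore, additional 18 patients need to be recruited at the second stage".

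Section 13.3.1 names the test: "the primary endpoint will be analyzed using the one-sided one sample t-Test with a significance level of 0.05". The Schema carries a different total, "Required sample size: 102", which section 13.2 does not derive.

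**The concern.** Once the pilot has been observed, its contribution to the final sample is a known count, not an expected one. The plan has 9 analyzable patients and needs 18, so the second stage must supply 9. Subtracting registrations from registrations (50 - 32) instead credits the pilot with the planned 36% yield, and so with patients it did not produce.

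The primary conclusion is one test in a single arm. Section 1.7 says the comparison with historical data is to help decide whether a phase III trial is warranted. If the expected sample is smaller than stated, a non-significant result will be read against a power that this recruitment does not deliver.

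**Working it through.** **Inputs.** Section 13.2: null mean decline 0.60, alternative 0.30 (difference 0.30), SD 0.51, one-sided alpha 0.05, 60% deaths, 10% in-evaluable, 32 enrolled, 9 analyzable. Section 13.3.1: one-sided one-sample t-test.

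**1. The plan's figures reproduce.**
- Normal approximation: n = ((1.645 + 0.842) x 0.51/0.30)^2 = 17.87, so 18, with power 80.3% at n = 18.
- Yield: 0.40 x 0.90 = 0.36.
- Registered: 18/0.36 = 50. Additional: 50 - 32 = 18.

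**2. What the subtraction assumes.** Analyzable patients credited to the pilot: 32 x 0.36 = 11.5. Reported: 9. Difference: 2.5.

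**3. Expected final sample at the plan's own yield.** 9 + 18 x 0.36 = 9 + 6.5 = 15.5. Reaching 18 needs at least 9 analyzable among the 18 new patients; the binomial probability at 0.36 is 16%.

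**4. Power**, with true mean decline 0.30 and SD 0.51:

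| Situation | Exact t | Normal approximation |
|---|---|---|
| n = 18 | 77.3% | 80.3% |
| 9 + binomial(18, 0.36), averaged | 70.8% | 74.4% |

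The gap from the stated 80% therefore has two parts. About 3 points (80.3 to 77.3) arise because n = 18 comes from the normal approximation while the test is a t-test. About 6.6 points by exact t (77.3 to 70.8), or 5.9 by the approximation (80.3 to 74.4), come from the subtraction.

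**5. Sensitivity: the pilot's yield persists.** 9/32 = 28.1% (exact 95% CI 14% to 47%). Expected total: 9 + 18 x 0.281 = 14.1. Averaged exact t power is 67%, and the chance of reaching 18 is 4%.

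**6. Sensitivity: j of the other 23 pilot patients were still pending.** If each pending patient has a 36% chance of becoming analyzable, the expected total is 9 + (18 + j) x 0.36:

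| j | Expected analyzable | Averaged power, exact t |
|---|---|---|
| 0 | 15.5 | 70.8% |
| 3 | 16.6 | 73.5% |
| 5 | 17.3 | 75.2% |
| 7 | 18.0 | 76.8% |

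At j = 7 the subtraction is exactly right, and the yield among patients with known status is 9/25 = 36%.

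**The case against.** **Pending patients.** This is the strongest objection. Section 13.2 describes the 32 as enrolled at baseline and does not say that all had passed the 3-month visit. If about 7 had not, there is no shortfall. This stands, and it makes the point conditional. But the plan mentions no pending patients and does not use them to justify the subtraction.

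**Attribution.** A reader might set 80% beside 67-71% and blame the whole difference on low yield. The documents do not support that: with a full 18 patients the named test already has only 77% power. Comparing like with like narrows the loss a little further. If the plan's 50 registrations are all treated as still unobserved at 36%, averaged exact t power is 76.3%, which leaves a loss of about 5.5 points.

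**The 36% rate.** A reader might also infer that the pilot disproved the planned yield and that keeping it was an error. It did not: 9 or fewer of 32 has probability 0.23 when the true yield is 36%, and the confidence interval includes 36%. If some patients were pending, 28% is also only a lower bound. Keeping 36% for future patients is defensible, so the 28% figures are a sensitivity case. The 15.5 does not depend on them, because it uses 36% for every new patient. Chance can explain why the pilot gave 9, but it does not supply the missing 2.5.

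**Conclusion.** The point holds in conditional form. Unless some of the 23 other pilot patients were still awaiting the 3-month test, 18 more registrations give an expected 15.5 analyzable patients at the plan's own yield, not 18. Power is then about 71% by exact t (74% by the plan's approximation). The subtraction accounts for about 6-7 points of the gap from 80%, and the approximation for about 3. If the pilot's 28% yield continued, the figures would be 14.1 patients and 67%.

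The result rests on three assumptions:
- No pilot patient was pending; about 7 pending would cancel the shortfall.
- Relative decline is close enough to normal for the t-test power formula.
- The 51% is an SD. Section 13.2 calls it a standard error when reporting the pilot and uses it as an SD in the calculation. As a true standard error from 9 patients it would imply an SD of 0.51 x 3 = 153%, and none of these power figures would apply.

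A reader might go further and question the validity of the test. Nothing here bears on the type I error; what is wrong is the stated analyzable number and power.

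**What to change.** In section 13.2:

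- State how many of the 32 were still awaiting the 3-month test when the 9 were counted.
- Derive the second stage from the 9 analyzable patients in hand (plus the expected yield of any pending), not from 50 - 32.
- If 50 registered is kept and none was pending, replace the stated 18 analyzable and 80% power with about 15-16 expected analyzable and about 71% power by exact t. Give 14 and 67% as the sensitivity case. This costs wording only.
- If the sponsor prefers to keep 18 analyzable, 9/0.36 = 25 more registrations (57 in all, 7 above the current target) reach it on average, with about 77% power by exact t. The chance of actually reaching 18 is then about 57%. To have 80% by exact t needs about 20 analyzable: 11/0.36 = 30.6, so 31 more registrations (63 in all). Either choice lengthens recruitment.
- Call the 51% an SD throughout, if that is what it is.

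Reconcile the 102 in the Schema with the 50 in section 13.2.
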